Pregnancy outcomes and medical costs according to gestational diabetes mellitus diagnostic criteria: randomized prospective study. POMECS study.

Protocol ID: 00003

Approval Number: 11/09/2016

Version: 8th January 2018

Due to Hyperglycemia and Adverse Pregnancy Outcomes study results, a new gestational diabetes mellitus (GDM) diagnostic criteria was defined using a one-step approach (75-g oral glucose tolerance test -OGTT-) ¹

However, not all scientific societies have accepted and have implanted this new diagnostic criteria. The lowest glycemia cut-off of this criteria regarding the two-step approach entails an increase in GDM incidence with discordant studies about its cost-effectivity ²⁻⁴.

It will be assessed if pregnancy outcomes and medical costs are different depending on diagnostic criteria used.

RESEARCH DESIGN AND METHODS

The POMECS study is a randomized, parallel group trial, conducted in Spain. The Ethics Committee at Hospital Universitari Mútua Terrassa (Spain) approved the study.

Participants:

All pregnant women with follow-up of their gestation at Hospital Universitari Mútua Terrassa (Spain), at first antenatal visit, will be proposed to participate in the study.

Inclusion Criteria:

- Age 18-50 years
- No expectation that the participant will be moving out of the area of the clinical centre during the next year
- Informed Consent Form signed by the subject

Exclusion Criteria:

- Pre-existing type 1 or 2 diabetes
- Advanced human immunodeficiency virus infection (on medications that cause hyperglycemia), severe liver disease, gastric bypass surgery or other illnesses/surgeries that preclude them from drinking the glucose solution.

Randomization:

All pregnant women without a former diagnosis of diabetes mellitus will be considered for gestational diabetes mellitus (GDM) screening at 24–28 weeks of gestation.

Women with risk factors for diabetes at their initial prenatal visit will be screening at 9-12 weeks of gestation. Risk factors are: Age >35years, obesity (body mass index $\geq 30\text{kg/m}^2$ or $>27.5\text{kg/m}^2$ in Asian Americans), first-degree relative with diabetes and high-risk race/ethnicity (e.g., African American, Latino, Native American, Asian American, Pacific Islander).

At the time of GDM screening, patients will be assigned a number by a random number generation program (ratio 1: 1) that will classify them to one of the following two groups:

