- Experimental Group (One-step): International Association of Diabetes and Pregnancy Study Groups (IADPSG) Criteria.

Performing a fasting 2 hour 75g OGTT. The diagnosis of GDM is made if at least one or more values are \geq : Fasting 92, 1-hour 180, or 2-hour 153 mg/dL.

- Active Comparator (Two-step): National Diabetes Data Group (NDDG) Criteria

Step 1: Performing a 1h 50-g glucose load test (nonfasting). If the plasma glucose level measured 1 h after the load is \geq 140 mg/dL, proceed to a 100-g OGTT.

Step 2: 100-g OGTT. The diagnosis of GDM is made if at least two of the following four plasma glucose levels measured (fasting, 1 h, 2 h, 3 h after the OGTT) are \geq : 105mg/dl, 190mg/dl, 165mg/dl and 145mg/dl respectively.

If only one value is exceeded, 100g OGTT will be repeated 2-3weeks after.

Pregnant women without GDM diagnosis at third trimester of pregnancy will repeat GDM screening (according previous randomization) if it appears macrosomia or/and polyhydramnios in the follow-up.

GDM diagnosed women will be managed with diet and self-monitoring of blood glucose. Insulin will be added according to the local protocol⁵. All women will receive routine prenatal care (without differences between randomized groups).

Outcomes

Primary outcome Measures:

Large for gestational age (LGA): Infant birthweight >90th centile using customized growth curves. Time Frame: At birth of infant.

Secondary Outcome Measures:

1. Infant outcomes

- Small for gestational age (infant birthweight <10th centile using customized growth curves); macrosomia (infant birthweight \geq 4kg), Neonatal obstetric trauma (shoulder dystocia, clavicle fracture, brachial plexus injury, intrapartum asphyxia), Congenital anomalies (Coding of EUROCAT), Pregnancy loss (Miscarriage, stillbirth, neonatal death)

Time Frame: At birth of infant

- Neonatal hypoglycaemia (neonatal plasma glucose levels <2.5 mmol/L in the first 24 hours of life and <2.8 mmol/L thereafter), Neonatal hypocalcemia (neonatal calcium levels <7mg/dl), Neonatal hyperbilirubinemia (hyperbilirubinemia treated with phototherapy), Neonatal polycythemia (hematocrit from a peripheral venous sample >65 percent), Respiratory Distress Syndrome (onset of progressive respiratory failure shortly after birth, in conjunction with a characteristic chest radiograph -after ruling out other causes-), Hypertrophic cardiomyopathy (increased left ventricular -LV- wall

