thickness ≥ 15 mm imaged anywhere in the LV wall -by transthoracic echocardiography-), NICU admission (NICU admission for treatment or surveillance), neonatal hospital stay (Length of hospital stay –days-).

Time Frame: at infant hospital discharge.

- Perinatal mortality (infant deaths that happen at less than 7 days of age and fetal deaths with a gestational age of 28 weeks or more). Time Frame: First 7 days postpartum.

2. Maternal outcomes

-Hypertension in pregnant: worsening of chronic hypertension, gestational hypertension and preeclampsia. Time Frame: First 3 months postpartum

- Polyhydramnios (Amniotic fluid index ≥ 25 cm). Time Frame: At birth of infant.

- Cesarean section delivery of a baby through a surgical incision in the mother's abdomen and uterus. Time Frame: At birth of infant.

- Maternal hospital stay: Length of hospital stay (days). Time Frame: at maternal hospital discharge.

- Questionnaires: Evaluation of Mediterranean diet adherence using Mediterranean Diet Adherence Screener (MEDAS) questionnaire. Evaluation of health-related physical activity using IPAQ questionnaire. Time Frame: up to 12-14weeks from last menstrual period.

3. Gestational age at delivery: Gestational age was defined as completed weeks based on last menstrual period or the earliest ultrasound assessment if discordant. Time Frame: At birth of infant.

4. Medical cost: economic cost include laboratory costs; glucose bottles (50 g, 100 g and 75 g); pharmaceutical expenditure (exact insulin doses consumed, total pens, needles, strips); medical visits during pregnancy and postpartum (endocrinologist, educational nurses, obstetrician and midwives); total number of tests (ultrasounds, cardiotocography records); cost of intensive care unit admissions (Length of stay and complexity) and total hospital admission costs. Time Frame: First 3 months postpartum

Statistical analysis

Sample size (n=3,644) was calculated to detect a 20% decrease rate of LGA (primary outcome), assuming baseline rate of 16.5% ($\alpha=0.05$ and $\beta=0.80$). This decrease rate was obtained from *St Carlos Gestational Diabetes Study*, carried out in Spanish population which compared Carpeten-Coustan criteria vs IADPSG criteria³. Since we will use NDDG criteria (vs. IADPSG), baseline LGA incidence was obtained from Spanish Multicentre Study⁶.

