Results will be presented as means \pm standard deviation in normal distribution, median [interquartile interval (IQI)] in non-normal distribution or percentages. Normal distribution will be tested for each variable using the Kolmogorov test.

Student t test will be used for normally distributed variables and the Mann-Whitney U test for non-normally distributed variables between two independent groups.

Proportions will be compared using a Pearson's chi-square or Fisher exact test as appropriate.

We will use logistic regression analyses or multivariate linear regression (as appropriate) to estimate the ratio of the probability [I-TDS(1)] of occurrence of an adverse event (primary and secondary outcomes) with 95% CIs by experimental group versus control group adjusting for confounding factors (age, smoke habit, weight, multiparity) P values <0.05 were considered statistically significant. All statistical calculations will be performed with the STATA 14.0 statistical package.

REFERENCES

1. Metzger, B. E. *et al.* Hyperglycemia and adverse pregnancy outcomes. *N. Engl. J. Med.* **358**, 1991–2002 (2008).
2. Meltzer, S. J., Snyder, J., Penrod, J. R., Nudi, M. & Morin, L. Gestational diabetes mellitus screening and diagnosis: A prospective randomised controlled trial comparing costs of one-step and two-step methods. *BJOG An Int. J. Obstet. Gynaecol.* (2010). doi:10.1111/j.1471-0528.2009.02475.x
3. Duran, A. *et al.* Introduction of IADPSG criteria for the screening and diagnosis of gestational diabetes mellitus results in improved pregnancy outcomes at a lower cost in a large cohort of pregnant women: the St. Carlos Gestational Diabetes Study. *Diabetes Care* **37**, 2442–50 (2014).
4. Corcoy, R., Lumberras, B., Bartha, J. L., Ricart, W. & Grupo Español de Diabetes y Embarazo. New diagnostic criteria for gestational diabetes mellitus after the HAPO study. Are they valid in our environment?. *Endocrinol. Nutr.* **57**,

277–80

5. Asistencia a la gestante con diabetes. Guía de práctica clínica actualizada en 2014. *Av. en Diabetol.* **31**, 45–59 (2015).
6. Ricart, W. *et al.* Potential impact of American Diabetes Association (2000) criteria for diagnosis of gestational diabetes mellitus in Spain. *Diabetologia* **48**, 1135–41 (2005).

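### MEDAS and IPAQ are listed as secondary outcomes but are due at least 10 weeks before women without risk factors are randomised

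*Combined protocol and SAP*

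**What the plan says.** All references are to the combined protocol and SAP.

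- **Secondary Outcome Measures, item 2 (Maternal outcomes).** MEDAS and IPAQ are grouped under one questionnaire entry with one time frame: "Evaluation of health-related physical activity using IPAQ questionnaire. Time Frame: up to 12-14weeks from last menstrual period". No later administration of either is described.
- **Participants.** Women are approached early: "at first antenatal visit, will be proposed to participate in the study". The gestational week of that visit is not given.
- **Randomization.** The moment of allocation is explicit: "At the time of GDM screening, patients will be assigned a number by a random number generation program (ratio 1: 1". Women without a previous diabetes diagnosis "will be considered for gestational diabetes mellitus (GDM) screening at 24–28 weeks of gestation". An earlier window applies to some: "Women with risk factors for diabetes at their initial prenatal visit will be screening at 9-12 weeks of gestation".
- **Management after diagnosis** (text following the two-step criteria). "GDM diagnosed women will be managed with diet and self-monitoring of blood glucose".
- **Statistical analysis.** Regression is to estimate the "occurrence of an adverse event (primary and secondary outcomes) with 95% CIs by experimental group versus control group". The covariates are named later in that same sentence: "adjusting for confounding factors (age, smoke habit, weight, multiparity". Significance is set at P<0.05. A separate sentence provides Student t or Mann-Whitney tests between two independent groups and names no variables. Nothing exempts MEDAS or IPAQ from comparison, and neither score is called a baseline variable or a covariate.

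**The concern.** An outcome has to be capable of responding to allocation. For women without risk factors, both scores fall due well before they are randomised. The only route the protocol describes from arm to diet is a diagnosis followed by diet management, and in these women that comes after the questionnaires.

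The risk is one of misreading. The protocol's introduction expects the one-step criteria to diagnose more women, and diagnosed women receive diet management. A chance imbalance in MEDAS could then be reported as a plausible diet response, and a null result as evidence that diet did not change. Neither conclusion could be drawn.

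Women screened early add a second problem. Their scores may be taken before or after allocation, so one variable could be baseline in some women and post-randomisation in others.

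**Working it through.** **Plan's own figure.** The plan gives no calculation for this point. Its sample size reproduces: 16.5% against 13.2% (0.165 × 0.80), two-sided α 0.05, 80% power, pooled variance and no continuity correction give 1,822 per arm, 3,644 in total. The point does not depend on it.

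**Same clock.** The questionnaire deadline is counted from last menstrual period. Gestational age is defined in the outcomes list in completed weeks from the same origin, or from the earliest ultrasound if discordant. The windows can be compared directly.

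**Women without risk factors.** Deadline 12–14 weeks; randomisation 24–28 weeks.

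- Shortest gap: 24 − 14 = 10 weeks.
- Longest gap from the deadline: 28 − 12 = 16 weeks.

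The time frame is only an upper limit, so actual completion may be earlier and the gap longer. No in-window value can follow allocation.

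**Women with risk factors, if randomised at their 9–12 week screen.** Deadline minus randomisation:

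- Smallest: 12 − 12 = 0 weeks.
- Largest: 14 − 9 = 5 weeks.

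A form may therefore precede allocation or follow it by up to 5 weeks.

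**Share of the outcome list**, counting each composite once:

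| Group | Count |
|---|---|
| Infant, at birth | 5 |
| Infant, at discharge | 8 |
| Perinatal mortality | 1 |
| Maternal, other than questionnaires | 4 |
| MEDAS, IPAQ | 2 |
| Gestational age at delivery | 1 |
| Medical cost | 1 |
| **Total** | **22** |

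The other 20 have time frames ending at birth, hospital discharge, 7 days or 3 months postpartum. Only these two close before some women are randomised.

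**Chance of a spurious finding.** Assume each score is tested once by arm at 0.05, on pre-randomisation values, among women as randomised. No true effect is possible, so:

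- Independent scores: 1 − 0.95² = 0.0975.
- Fully dependent scores: 0.05.
- Upper bound for any correlation: 0.05 + 0.05 = 0.10.

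If women are lost after allocation, a difference among those analysed could also reflect selective loss. It still could not be a response.

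**The case against.** The timing conflict itself is hard to dispute. The case on the other side concerns how much it matters.

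- *It is a labelling slip.* The early time frame is printed beside the instruments, the stated aim is pregnancy outcomes and cost, and no diet or activity hypothesis appears. This limits the damage. But the label decides what is analysed and reported as an outcome, and nothing in the plan corrects it.
- *The test is inferred.* The regression sentence speaks of adverse events, which the scores are not. This stands: a planned test is a reading and not an explicit statement. The reading is reasonable, because the sentence covers secondary outcomes without exception and the t or Mann-Whitney sentence suits continuous scores.
- *The 5% to 10% figure is conditional.* This also stands. No analysis by risk group is described, so a real comparison would pool women with mixed timing. The share with risk factors is not given and the risk list is broad. Scoring is not specified either, so two tests is an assumption.
- *The count of 22 depends on how composites are split.* True; it locates the problem and does not measure its impact.
- *Leaving the scores out of the adjustment list is discretionary.* Agreed. It shows only that the plan does not treat them as baseline.
- *Requiring early completion may create missing forms.* It may, in women screened from week 9. Recording the completion date relative to randomisation would be lighter, but alone it leaves the scores listed as outcomes.

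**Conclusion.** The concern holds. In women without risk factors, MEDAS and IPAQ are baseline measurements listed as outcomes, with the deadline 10 to 16 weeks before allocation. Among all such women as randomised, any difference between arms is chance. In women with risk factors the status of the scores is undetermined, on the assumption that these women are randomised at the early screen.

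The reach is limited to 2 of 22 secondary outcomes. The timing conclusion rests only on the protocol's own windows and is firm. The claim that the scores would be tested is a reading of the analysis section, and the 5% to 10% false-positive chance applies only under the conditions given with it. The change should be made, but nothing about the primary analysis, sample size or power depends on it.

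**What to change.** 1. Move MEDAS and IPAQ from Secondary Outcome Measures to baseline characteristics.
2. State that both are completed before randomisation in all women, for example at the first antenatal visit, and record the completion date so that late forms can be identified.
3. Describe the scores by arm without a between-arm test.
4. If they are to serve as prognostic covariates, prespecify this and use only pre-randomisation values.
5. Optional: if a diet or activity response is of interest, add an assessment at a stated time after randomisation for all women, with the early score as its baseline.

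Items 1 to 4 cost an edit to the outcome list (22 to 20 secondary outcomes) and a few lines on timing and use, with no extra participants or procedures. The practical burden is in women screened from week 9. The protocol gives no week for the first antenatal visit and does not say that consent is signed there, so some forms may arrive after allocation and would count as missing baseline values. Item 5 costs one further round of questionnaires.

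### Medical cost is a headline aim, but the plan does not say which analysis is the cost result, and its general rule leads to medians and a Mann-Whitney test instead of mean cost

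*Combined protocol and SAP*

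**What the plan says.** The title is "Pregnancy outcomes and medical costs according to gestational diabetes mellitus diagnostic criteria", and the introduction states the aim: "It will be assessed if pregnancy outcomes and medical costs are different depending on diagnostic criteria used". As background, it says that the lower cut-off "entails an increase in GDM incidence with discordant studies about its cost-effectivity". Secondary Outcome Measures, item 4, lists the components of medical cost up to three months postpartum, among them intensive care and hospital admissions. It does not say what is compared between arms.

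The Statistical analysis section never mentions cost. Three general statements bear on it:

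- The gate: "Normal distribution will be tested for each variable using the Kolmogorov test".
- What follows from the gate: mean and standard deviation with a t test if normal; otherwise "median [interquartile interval (IQI)] in non-normal distribution or percentages" and the rank test ("Student t test will be used for normally distributed variables and the Mann-Whitney U test for non-normally distributed variables between two independent groups").
- The adjusted analysis: "We will use logistic regression analyses or multivariate linear regression (as appropriate) to estimate the ratio of the probability" of an adverse event, for primary and secondary outcomes, with 95% CIs, adjusted for age, smoking, weight and multiparity.

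**The concern.** The quantity that tells a health service which strategy costs more is the arithmetic mean, because total spend is the mean times the number of women. Under the general rule the unadjusted cost result would be a pair of medians and a rank test, and no mean would be presented.

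This trial has the structure in which ranks and means can part. One-step criteria raise GDM incidence, which adds a moderate cost to many women. Any saving may come from a few very expensive admissions. A rank test registers the first and largely ignores the size of the second. Since two analyses could each be called the cost result and neither has priority, the choice could be made after the data are seen.

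**Working it through.** **1. Size of the comparison.** With p1 = 0.165, p2 = 0.165 × 0.8 = 0.132, mean 0.1485, two-sided α = 0.05, and the printed β = 0.80 read as power:

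n = [1.960·√(2 × 0.1485 × 0.8515) + 0.842·√(0.165 × 0.835 + 0.132 × 0.868)]² / 0.033² = (0.986 + 0.423)² / 0.001089, which is 1,822 per arm after rounding up (unrounded terms), or 3,644 in total.

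This matches the plan. The sample size is not in dispute.

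**2. Where the rule sends cost.** The plan does not say that costs are skewed; that is inferred from the admission components. At 1,822 per arm the Kolmogorov test rejected normality in 200 of 200 simulated trials in each of nine scenarios. With a second set of assumed costs it rejected in every one of 300 trials in each of four scenarios.

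**3. Can ranks and means disagree?** The documents give no costs, GDM rates or NICU rates, so every input here is assumed, in arbitrary units:

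- base cost lognormal, median 3,000, log-SD 0.25, 0.4 or 0.6
- GDM care +1,000; NICU stay +10,000
- two-step arm: GDM 10%, NICU 5%
- one-step NICU rate set so that the two means are equal

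For example, GDM 15% adds 0.05 × 1,000 = 50, and NICU 4.5% removes 0.005 × 10,000 = 50. Screening costs are varied because "glucose bottles (50 g, 100 g and 75 g") fall on different women: the 75-g test on the one-step arm, the 50-g test on the two-step arm, and the 100-g test only on two-step women with a 50-g result of at least 140 mg/dL.

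Share of 4,000 trials in which Mann-Whitney calls one-step dearer, at the three log-SDs:

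| Screening-cost difference | One-step GDM | One-step NICU | One-step dearer |
|---|---|---|---|
| None | 15% | 4.5% | 24.0 / 13.0 / 7.9% |
| None | 20% | 4.0% | 74.0 / 38.3 / 18.6% |
| +60 in a quarter of two-step women | 15% | 4.65% | 13.3 / 8.6 / 5.3% |
| +60 in a quarter of two-step women | 20% | 4.15% | 59.0 / 28.1 / 13.7% |
| Two-step +40 for every woman | 15% | 4.9% | 4.1 / 3.5 / 3.6% |
| Two-step +40 for every woman | 20% | 4.4% | 31.7 / 15.5 / 10.0% |
| Two-step +80 for every woman | 15% | 5.3% | 0.2 / 0.7 / 1.3% (cheaper: 14.4 / 7.4 / 4.9%) |
| Two-step +80 for every woman | 20% | 4.8% | 5.8 / 5.5 / 3.9% |
| One-step +30 for every woman | 15% | 4.2% | 56.9 / 26.1 / 12.7% |

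A Welch t test on the same data gave 1.8 to 3.1% in each direction throughout.

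The second set of costs (base mean 2,000, GDM +500, mean admission 10,000) lets the means differ. With GDM 35% against 10% and admissions 3% against 5%, the means are 2,000 + 175 + 300 = 2,475 and 2,000 + 50 + 500 = 2,550. One-step is cheaper, yet Mann-Whitney was significant for one-step higher in 99.7% of 300 trials. With admissions equal at 5% the means are 2,675 and 2,550, and the two measures agree in direction.

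**4. Precision of the mean difference.** At log-SD 0.25 the base-cost variance is 3,095² × (e^0.0625 − 1) ≈ 617,900.

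- Two-step: 617,900 + 90,000 (GDM) + 4,750,000 (NICU) = 5,457,900
- One-step (GDM 20%, NICU 4.0%): 617,900 + 160,000 + 3,840,000 = 4,617,900
- SE = √(10,075,800 / 1,822) = 74.4
- 95% half-width: 1.96 × 74.4 = 146
- Difference with 80% power: 2.80 × 74.4 = 208

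Across the scenarios the half-width is 146 to 211 and the 80%-power difference about 210 to 300, if every NICU stay costs the same. If NICU cost varies (lognormal, log-SD 1, same mean), simulation gives about 225 to 285 and 320 to 405. Two-step mean costs are 3,695, 3,850 and 4,192, so the detectable difference is roughly 6% (210 / 3,695) to 10% (405 / 4,192) of the mean.

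**5. Does the proposed method hold its level?** Four equal-mean settings, 600 trials each, using regression on arm and four covariates with a within-arm percentile bootstrap: the 95% CI excluded zero in 6.2, 3.8, 3.3 and 5.2%. The simulation error around 5% is ±1.96 × √(0.05 × 0.95 / 600) = ±1.7 points, so these fit the nominal level.

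**The case against.** The strongest reply is that the plan already contains the right estimator. Linear regression is offered for secondary outcomes with 95% CIs, cost is a continuous secondary outcome, and the arm coefficient is an adjusted mean cost difference. The probability-ratio wording fits no linear regression and may be loose drafting. This largely stands. A reader might infer that the plan cannot produce a mean cost difference; the documents do not support that. What remains is that the plan does not make this the cost result, while an explicit rule for every variable points elsewhere.

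A second reply is that the objective asks only whether costs differ, which a rank test addresses. That also stands in part. A Mann-Whitney rejection here would not be a false positive, because the cost distributions do differ. The simulated percentages measure disagreement between two questions, not an error rate. But a rank test does not settle which strategy costs more in total, and the introduction frames the issue as one of cost-effectiveness.

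A third reply is that the magnitudes depend on assumptions. That stands in full. The 74% needs GDM to double, NICU admissions to fall by just enough to equalize means, no screening-cost difference and the smallest spread.

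**Conclusion.** The point holds as a gap in the cost analysis that should be fixed. The general rule would almost certainly give cost an unadjusted rank test with no mean per arm, and nothing names the regression mean difference as the cost result. That conclusion rests on the text and on the expected skew of admission costs.

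The size of any disagreement cannot be derived from the documents. Under the assumed costs, with equal means, Mann-Whitney favours one-step dearer in anything from 0.2% to 74% of trials, and it can also point to cheaper. A reader might infer that the trial is likely to report the wrong direction on cost. The documents do not support this: if NICU admissions do not fall and screening costs are equal, one-step really is dearer and Mann-Whitney points the right way. The LGA analysis and the sample size are untouched.

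**What to change.** Add to the Statistical analysis section:

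> Medical cost is exempt from the normality-test rule. The cost result is the between-arm difference in arithmetic mean cost per randomized woman, from the planned linear regression (age, smoking, weight, multiparity), with a 95% CI robust to skew, for example a non-parametric bootstrap within arm. The unadjusted mean difference is reported alongside. Medians are descriptive, and no conclusion on cost rests on the Mann-Whitney test.

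This needs a few lines of Stata, no new data, and no change to the sample size or the LGA analysis. The number of bootstrap replicates and the type of interval are for the trial statistician to choose. The text does not settle how the cost components are priced and combined, or how women with incomplete cost or covariate data are handled; both should be stated with it.

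The downside is a wide interval. Under the assumed costs it is about ±146 to 211 per woman with a fixed NICU cost, or ±225 to 285 with a varying one, and 80% power is reached only for differences of about 6 to 10% of mean cost. A significant cost result may therefore be less likely, but the width reflects real uncertainty about mean cost.

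### The plan labels the logistic-regression result for LGA a probability ratio, but that model gives an odds ratio and no step to a risk ratio is planned (minor, wrong as written).

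*Combined protocol and SAP*

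**What the plan says.** The primary outcome, under Outcomes, is binary: "Large for gestational age (LGA): Infant birthweight >90th centile using customized growth curves".

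The Statistical analysis section sizes the trial on it: "Sample size (n=3,644) was calculated to detect a 20% decrease rate of LGA (primary outcome), assuming baseline rate of 16.5" per cent.

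For the analysis, the same section plans three things that bear on LGA:

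- **Description.** Categorical results are summarised as percentages: "median [interquartile interval (IQI)] in non-normal distribution or percentages".
- **Unadjusted test.** "Proportions will be compared using a Pearson's chi-square or Fisher exact test as appropriate". No effect measure or interval goes with this test.
- **Adjusted estimate.** "We will use logistic regression analyses or multivariate linear regression (as appropriate) to estimate the ratio of the probability [I-TDS(1)] of occurrence", and the sentence continues "of occurrence of an adverse event (primary and secondary outcomes) with 95% CIs by experimental group versus control group", adjusting for age, smoking, weight and multiparity. This is the only between-arm estimate for which a CI is planned.

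The terms odds ratio, risk ratio and risk difference appear nowhere in the document. Nor does any method for getting a risk ratio, such as marginal standardisation, a log-binomial model or modified Poisson regression.

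**The concern.** A ratio of two probabilities is a risk ratio. The exponentiated arm coefficient of a logistic model is an odds ratio. The plan joins the first name to the second model and gives no step between them, so the text does not settle which quantity will be printed for the primary outcome.

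At an LGA rate near 16.5% the two measures differ visibly, and the odds ratio lies further from 1. An odds ratio reported under the plan's label would make the benefit of one-step screening look larger than the risk reduction observed. It would also be on a different scale from the effect the trial was sized to detect. What is at stake is how readers interpret the adjusted estimate, not whether the trial's test is valid.

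**Working it through.** **Inputs from the plan.** Control LGA rate 16.5%; 20% decrease; 1:1 allocation; alpha 0.05; total N 3,644. The plan prints 0.80 as beta. It is used here as the power, because that reading reproduces N. The plan does not state sidedness; two-sided reproduces N.

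**1. Reproduce the sample size.** With p1 = 0.165, p2 = 0.8 × 0.165 = 0.132 and mean p = 0.1485, the pooled two-proportion formula is

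n per arm = [1.960 × √(2 × 0.1485 × 0.8515) + 0.8416 × √(0.165 × 0.835 + 0.132 × 0.868)]² / 0.033² = 1,821.5.

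That rounds up to 1,822 per arm, and 2 × 1,822 = 3,644, an exact match.

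**2. Confirm the scale of the 20%.** If it were an odds ratio of 0.80, the one-step odds would be 0.8 × 0.165/0.835 = 0.1581, a risk of 13.65%. The same formula then needs 2,474 per arm, 4,948 in total, and power at 3,644 would be about 67%. So the design effect is a relative risk reduction.

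**3. The measures at the design values** (1,822 per arm, about 301 and 241 LGA infants, unadjusted, large-sample intervals):

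| Measure | Formula | Estimate | SE | 95% CI |
|---|---|---|---|---|
| Risk ratio | 0.132/0.165 | 0.80 | 0.0799 (log) | 0.684 to 0.936 |
| Odds ratio | (0.132/0.868)/(0.165/0.835) = 0.1521/0.1976 | 0.770 | 0.0937 (log) | 0.641 to 0.925 |
| Risk difference | 0.132 − 0.165 | −3.3 points | 1.18 points | −5.6 to −1.0 |

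Read as a probability ratio, the odds ratio suggests a reduction of 1 − 0.770 = 23%. The risk reduction is 20%.

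**4. Effect on significance.** z = ln(0.80)/0.0799 = −2.79 for the risk ratio and ln(0.7696)/0.0937 = −2.80 for the odds ratio, so practically none.

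**5. Effect of covariate adjustment.** The planned estimate is adjusted, which moves an odds ratio further from 1 even with both arm risks fixed. The document gives no covariate effects, so let s be the assumed SD of the covariates' combined log-odds. Solve for the intercepts at which the mean of expit(a + sZ), Z standard normal, equals 0.165 and 0.132; the adjusted odds ratio is exp(a2 − a1), where a1 and a2 are the two-step and one-step intercepts.

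| Assumed s | Adjusted OR | Reads as | Standardised RR |
|---|---|---|---|
| 0 | 0.770 | 23% | 0.80 |
| 0.25 | 0.768 | 23% | 0.80 |
| 0.5 | 0.763 | 24% | 0.80 |
| 1.0 | 0.744 | 26% | 0.80 |

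**6. Other binary outcomes.** For a risk ratio of 0.80, the odds ratio is 0.798 at an assumed 1% baseline, 0.792 at 5% and 0.737 at 30%. Rare outcomes such as perinatal mortality are therefore hardly affected, and common ones are affected more than LGA.

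**7. Interval scale for the fix.** A symmetric delta-method interval on the ratio itself would be 0.80 ± 1.96 × 0.80 × 0.0799 = 0.675 to 0.925. The log-scale interval is 0.684 to 0.936. The two differ enough that the plan should say which is used.

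**The case against.** The strongest reply is that the phrase is loose wording for odds ratio. The plan names logistic regression, the usual ratio from that model is an odds ratio, and a bracketed marker that looks like a leftover comment sits on these very words. A correctly labelled adjusted odds ratio, shown beside the percentages, would be a valid analysis. All of this stands, and it is why the point is minor. It does not remove the mismatch, because the literal words still describe a different quantity from the one the model delivers.

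The reply that the gap is small also stands: 23% against 20% at the design values, with no change to the test. The 26% figure needs s = 1.0, which nothing in the document supports, so it should not be quoted as the expected size.

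Two stronger readings are tempting, and the document supports neither:

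- *The sponsor will report an odds ratio as a risk ratio, so the primary result will be wrong.* The plan does not show this. The harm arises only if the odds ratio is printed under the plan's label. Even then the chi-square test, the power and N are untouched, and the percentages in each arm let a reader work out the crude risk ratio.
- *The plan intends a probability ratio from linear regression, for example for "Maternal hospital stay: Length of hospital stay (days").* That is too literal. The sentence says the model is chosen as appropriate and refers to an adverse event, so the linear model is naturally read as serving the continuous outcomes. Naming its output a mean difference is tidying, not the correction of an error.

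**Conclusion.** Minor, but wrong as written. The plan promises a probability ratio for LGA from a model that directly gives an odds ratio, with no step between them, while the sample size rests on a relative risk reduction. The mismatch is worth 3 percentage points of apparent reduction at the design values (OR 0.770 against RR 0.80). It is worth about 4 points after adjustment if the covariates are moderately prognostic (s near 0.5, OR 0.763). The first figure rests only on the plan's 16.5% and 20%; the second depends on an assumed covariate strength that the document does not give. The intervals shown are unadjusted and illustrative.

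**What to change.** Replace the regression sentence with:

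> *For LGA we will report the percentage in each arm and, from the logistic model with age, smoking, weight and multiparity, the standardised adjusted risk ratio (CI computed on the log scale) and risk difference, one-step vs two-step, with 95% CIs. Any odds ratio reported, for LGA or for secondary outcomes, will be labelled as an odds ratio, and linear-regression results as mean differences.*

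Keep the chi-square, Fisher and Mann-Whitney tests as planned. Curing this defect needs no event-count threshold, no separate interval method for rare outcomes and no designated headline estimate.

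In Stata 14, with arm coded 0/1: fit `logit` with `i.arm` and the four covariates; run `margins arm, post`; then `nlcom ln(_b[1.arm]/_b[0bn.arm])`, exponentiating the estimate and its limits, and `lincom _b[1.arm]-_b[0bn.arm]`.

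The cost is a few more lines of code and a ratio slightly closer to 1 (0.80 instead of 0.77 at the design values). No new data are needed, and N does not change. A borderline adjusted interval can disagree with the unadjusted chi-square test, as it already can under the current plan.
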